4.3 Endpoint

4.3.1 Primary Efficacy Endpoint

The primary efficacy endpoint is the Overall Response Score (ORS) at Week 52.

ORS is a composite score derived from 4 components:

- Expanded Disability Status Scale (EDSS)
- Timed 25-Foot Walk (T25FW)
- 9-Hole Peg Test in the dominant hand (9HPT-D)
- 9HPT in the non-dominant hand (9HPT-ND)

The EDSS + is a composite derived from the EDSS, T25FW, 9HPT-D and 9HPT-ND where responder status is defined as a clinical meaningful improvement on one or more of these endpoints. Hereafter, the EDSS, T25FW, 9HPT-D and 9HPT-ND will also be referred to as "components of the EDSS +" or "components of the ORS."

The ORS is scored with a range from -4 to +4 at each assessment for all post-baseline visits. Scores for each component are assessed relative to their baseline value: -1 if there is clinically significant worsening, 0 if the change does not meet the clinically significant threshold criteria, or +1 if there is clinically significant improvement. The scores for all components are summed at each assessment. If any of the 4 components of the ORS are missing within a visit window, then the ORS will be considered missing for that visit.

The clinically significant change thresholds for EDSS, T25FW and 9HPT are provided in the following table.

	Score of ORS Components at Post-Baseline Visits			
ORS Components	-1 (Clinically Significant Worsening)	0 (No Clinically Significant Change)	l (Clinically Significant Improvement)	
EDSS change from baseline	\geq 1 if baseline EDSS \leq 5.5; \geq 0.5 if baseline EDSS \geq 6.0	-0.5, 0 or 0.5 if baseline EDSS $\leq 5.5;$ 0 if baseline EDSS ≥ 6.0	≤ -1 if baseline EDSS ≤ 5.5 ; ≤ -0.5 if baseline EDSS ≥ 6.0	
T25FW change from baseline	≥20%	> -20% and < 20%	\leq -20%	
9HPT-D change from baseline	\geq 20%	> -20% and < 20%	\leq -20%	
9HPT-ND change from baseline	≥20%	> -20% and < 20%	\leq -20%	

4.3.2 **Secondary Efficacy Endpoints**

The secondary efficacy endpoints include:

- Disability improvement responder status (Yes or No) on the EDSS+
- ORS at Weeks 12, 24, and 36

Exploratory Efficacy Endpoints 4.3.3

The exploratory efficacy endpoints include:

- Disability improvement response rate on the EDSS, T25FW, 9HPT-D, and 9HPT-ND at Weeks 12, 24, 36, and 52, and the EDSS + at Weeks 12, 24, and 36.
- Change from Baseline on the T25FW, 9HPT-D, 9HPT-ND at Weeks 12, 24, 36, and 52

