4.7 Missing Data Imputation

For continuous efficacy variables, data will be summarized using a mixed-effect model for repeated measures (MMRM) model unless otherwise specified. Missing data will not be imputed before applying an MMRM model.

The MMRM model relies on a missing at random (MAR) assumption.

For sensitivity analyses of the primary and secondary efficacy variables, missing values will be imputed using multiple imputation (MI) and categorized as responder/non-responder after imputation. The MI model also relies on a MAR assumption.

Justification for the MAR Assumption:

The COVID-19 pandemic is interfering with the conduct of many ongoing trials, with potential impact on treatment duration and the collection, analysis and the interpretation of clinical trial data. Some protocol-specified visits in this clinical trial may be impacted due to COVID-19 infection or logistical restrictions during the pandemic. For example, some scheduled visits may be missed due to self-quarantine or local government restrictions on travel; some visits may also be delayed or canceled due to healthcare resource constraints during the pandemic. These missed visits will be recorded in the database. The probability of having missed visits and missing data due to COVID-19 infection or logistical restrictions related to the COVID-19 pandemic can be reasonably assumed to be unrelated to the unobserved values conditional on the observed data. Therefore, for the purpose of statistical analysis, it is reasonable to assume that these missing data are missing at random (MAR) and the statistical models that require MAR assumption are appropriate. In some cases, sensitivity analyses may be performed to assess the impact of missing data and the robustness of the conclusion.

Where noted, summaries as observed will not impute values for missing evaluations, and thus a subject who does not have an evaluation on a scheduled visit will be excluded from the as observed for that visit.

Safety variables will be summarized as observed.

5.0

Analysis Sets and Important Subgroups

5.1 **Analysis Sets**

The Modified Intent-to-Treat (mITT) Population includes all randomized subjects who receive at least 1 dose of study drug. Subjects will be grouped according to treatment as randomized. The mITT analysis set will be used for all demographic and efficacy analyses, unless otherwise noted.

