9.2 Primary Efficacy Analysis

The primary efficacy variable is the ORS at Week 52 and secondary efficacy variables are the ORS at Weeks 12, 24, and 36. The ORS will be summarized continuously as observed (including n, mean, standard deviation, minimum, median and maximum) at each visit.

The frequency and percentage of subjects with each ORS score in the range of -4 to +4 will also be provided by treatment group at each visit. The data will be analyzed and summarized as observed, i.e., no imputations will be implemented.

The comparisons between the each elezanumab group and placebo for the primary efficacy endpoint ORS at each scheduled visit during the study will be performed using an MMRM. The ORS for each treatment group at scheduled visits and overall will be estimated from the model. The within group LS mean 95% confidence interval, pooled standard deviation, effect size, and 95% confidence interval for the effect size will also be presented by treatment group. The model will include the fixed effects of treatment, visit, diagnosis of MS (PPMS or nrSPMS), and background MS immunotherapy (Yes or No), and the treatment-by-visit interaction with baseline scores (EDSS, T25FW, 9HPT-D, 9HPT-ND) as covariates. The REPEATED statement will be used for visit with blocks in the covariance matrix identified by subject nested within treatment group. The unstructured covariance structure will be used to estimate the within subject variance-covariance. If the model fails to converge, the first order autoregressive (AR[1]) covariance structure will be substituted. If the model still fails to converge, the compound

symmetry (CS) covariance structure will be substituted. Denominator degrees of freedom will be computed using the Kenward-Roger method.

This will be repeated for the RF and MMIA sets.

The posterior probability that each elezanumab group's effect size is greater than 0.1, 0.3, and 0.5 will be presented for the mITT analysis set.

The ORS and corresponding 95% confidence interval based on the MMRM for the mITT analysis set will be plotted at each time point during the treatment period by treatment group.

The post-treatment ORS scores will be summarized continuously as observed.

9.3 **Secondary Efficacy Analyses**

Disability improvement on the EDSS + indicates clinically significant improvement on at least 1 of the components of the EDSS + (EDSS, T25FW, 9HPT [either hand]) as defined by the clinically significant change thresholds in Section 4.3.1).

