Improvement responder status on the EDSS + and each of its components will be analyzed by time point based on the criteria in Section 4.3.1. No confirmation will be required, i.e., improvement at the analysis time point only is required to be considered a responder.

The analysis will be presented at each time point with the number and percentage of responders, and the 95% confidence interval for the proportion of subjects based on Wald confidence limits, and the odds ratio and corresponding 95% confidence interval based on the logistic regression model including baseline as a covariate and treatment as a main effect. The model for the EDSS + will include the baseline EDSS, baseline T25FW, baseline 9HPT-D, baseline 9HPT-ND as covariates and treatment as a main effect. This will be presented based on the mITT, RF and MMIA analysis sets using non-responder

imputation. The logistic regression analysis will be repeated for the mITT analysis set based on the same multiple imputation as detailed in Section 9.3.1.

A summary of the improvement responder status on the EDSS + and each of its components will be presented for the mITT analysis set as observed.

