9.3.1 Sensitivity Analysis of the Primary and Secondary Endpoints

The primary and secondary endpoint analyses will be repeated for the RF and MMIA analysis sets as noted those respective sections.

Additionally, the analysis of ORS at Weeks 12, 24, 36, and 52, and the number and percentage of subjects with 12- and 24-week confirmed improvement for the EDSS+ and each of its components will be repeated based on multiple imputation (MI). First, a full dataset will be imputed using full data imputation MCMC. Data will be imputed for the EDSS, T25FW, 9HPT-D and 9HPT-ND in a continuous fashion for each endpoint separately. Then, the definition of clinically significant improvement/no change/clinically significant worsening as seen in Section 4.3.1 will be applied to determine the components of the ORS or 12- or 24- week confirmed improvement status. The imputation model will include treatment group, type of MS, baseline use of immunomodulator therapies, baseline variable for the respective endpoint being imputed, and the non-missing post-baseline values for the variable that will be imputed (value at Week 12, 24, 36, 52, 64 and 76). The number of imputed datasets will be 30, and the random seed will be 123455. The ORS at each visit noted above will be summarized for each treatment group and compared to placebo using ANCOVA, with baseline values for each component of the EDSS + included in the model. The responder status with 12- and 24-week confirmed improvement will be analyzed with a logistic regression as noted in Section 9.4.1.

M14-397 – Statistical Analysis Plan Version 2.0 – 06 Jan 2021

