9.4.1 Confirmed Improvement on the EDSS + and its components

Confirmed 12-week disability improvement on the EDSS + or components of the EDSS + indicates a subject has clinically significant improvement at a visit as well as the next visit for one or more EDSS + components, or if the next visit is missing, the subsequent visit. Confirmation may include assessments collected in the post-treatment follow-up period. The improvement confirmation must be in the same component of the EDSS +. If a subject has improvement in more than one component of the EDSS +, the subject must have confirmation in at least one of the same components to be considered as having confirmed disability improvement. For example, if a subject has clinically significant improvement in the T25FW at Week 12, the subject must have clinically significant improvement in the same component of the EDSS + at Week 24 (or if Week 24 is missing, Week 36) to be considered to have confirmed improvement.

Confirmed 24-week improvement on the EDSS + or components of the EDSS + indicates a subject has clinically significant improvement at 3 consecutive visits, or if one of the two subsequent visits are missing, subject demonstrates clinically significant

improvement at two of the subsequent three visits. Improvement status after confirmed improvement is not considered, i.e., if a subject has disability improvement in one component of the EDSS + at Week 12 and Week 24, then this subject is considered to have 12-week confirmed disability improvement regardless of a Week 36 status of clinically significant worsening, no clinically significant change, or clinically significant improvement.

The 12-week and 24-week confirmed disability improvement response rate will be summarized for the study for the EDSS +, as well as each of the individual components for the mITT, RF, and MMIA analysis sets based on a non-responder imputation. The frequency and percentage will be provided by treatment group. The treatment comparison will be conducted using the logistic regression model adjusted for the stratification factors and baseline scores associated with the endpoint. The proportion of responders, difference in responder rate, and 95% confidence interval for the responder rate based on Wald confidence limits will be presented based on the univariate summary. The odds ratio, and 95% confidence interval will be derived from the logistic regression model.

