The analyses for confirmed disability improvement will be repeated for the RF and MMIA analysis sets as noted those respective sections.

9.4.2 **Disability Progression**

Disability progression on the EDSS + indicates clinically significant worsening on at least 1 of the components of the EDSS + (EDSS, T25FW, 9HPT [either hand]) as defined by the clinically significant change thresholds in Section 4.3.1). This will be based on the imputed dataset described in Section 9.3.1.

Progression on the EDSS + and each of its components will be analyzed by time point based on the criteria in Section 4.3.1. No confirmation will be required, i.e., progression at the analysis time point only is required.

The analysis will be presented at each time point with the number and percentage of subjects, and the 95% confidence interval for the proportion of subjects based on Wald

confidence limits, and the odds ratio and corresponding 95% confidence interval based on the logistic regression model including baseline as a covariate and treatment as a main effect.

9.4.3 **T25FW**

The change from baseline in the T25FW during the Treatment Period will be analyzed using an MMRM. In addition to the summaries noted in Section 9.1, the pooled standard deviation, effect size, and 95% confidence interval of the effect size will be noted.

9.4.4 9HPT

The change from baseline in the 9HPT-D and 9HPT-ND during the Treatment Period will be analyzed using an MMRM. In addition to the summaries noted in Section 9.1, the pooled standard deviation, effect size, and 95% confidence interval of the effect size will be noted.

9.4.5 **Exploratory Patient and Clinician Measured Scales**

The change from baseline in the total score for the MSIS-29, the total score for the BAC -Tower of London, the total score for the BAC - Verbal Memory, BAC - Tower of London T-score, BAC - Verbal Memory T-score, and the overall symptom score and most bothersome symptom score for the MSIOA will be analyzed at the collected time points using an MMRM.

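### The ORS is set to missing when any component is missing, with no stated exception for a timed test the subject cannot complete because of MS disability (minor)

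*SAP*

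**What the plan says.** SAP 4.3.1 scores each of four components (EDSS, T25FW, 9HPT dominant hand, 9HPT non-dominant hand) as -1, 0 or +1 from its measured change against baseline, and sums them. For the timed tests a slowing of 20% or more scores -1. For EDSS the worsening threshold is 1 point, or 0.5 point from a baseline of 6.0 or more. The rule for gaps is: "If any of the 4 components of the ORS are missing within a visit window, then the ORS will be considered missing". It does not distinguish reasons, and the threshold table has no entry for a test that was not completed. Protocol 3.2 and 7.3 add nothing on this.

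For the primary analysis, SAP 9.2 states: "The data will be analyzed and summarized as observed, i.e., no imputations will be implemented". SAP 4.7 says that the MMRM relies on missing at random (MAR). The missing-data sensitivity analysis specified for ORS is the multiple imputation (MI) in SAP 9.3.1: "Data will be imputed for the EDSS, T25FW, 9HPT-D and 9HPT-ND in a continuous fashion for each endpoint separately". SAP 4.7 adds: "The MI model also relies on a MAR assumption". The written defence of MAR is that missingness from COVID-19 infection or pandemic logistics "can be reasonably assumed to be unrelated to the unobserved values conditional on the observed data". No other reason for missingness is argued.

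The SAP departs from MAR nearby. EDSS+ improvement (SAP 9.3) is "presented based on the mITT, RF and MMIA analysis sets using non-responder" imputation, and confirmed improvement (SAP 9.4.1) is summarised "for the mITT, RF, and MMIA analysis sets based on a non-responder imputation". Progression (SAP 9.4.2) goes back to the MI: "This will be based on the imputed dataset described in Section 9.3.1".

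**The concern.** A component can be missing because of the very outcome it measures. Protocol 5.1 admits subjects with baseline EDSS up to 6.5, and the disease is progressive over a 52-week study, so inability to finish a walk or peg test is foreseeable. Take a subject with baseline EDSS 6.0 who rises to 6.5 and cannot finish the walk at Week 52. The EDSS change earns -1, but that visit's ORS is blank. A subject who merely walks 20% slower keeps a -1.

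The first subject then contributes to the Week 52 estimate only through earlier visits, under MAR. The MI does keep the observed EDSS score and can impute a walk time that scores -1. But it imputes each component separately, from treatment group, MS type, baseline immunomodulator use and that component's own baseline and post-baseline values, so the EDSS worsening seen that day does not inform the missing walk. The relapse-free and minimal-missed-infusion repeats change the analysis set, not the assumption. SAP 4.7 allows further sensitivity analyses but names none. So no specified ORS analysis tests whether inability matters.

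**Working it through.** **1. The plan's own figure.** SAP 4.4 gives about 80% power for an effect size (ES) of 0.59, one-sided alpha 0.1, about 30 per arm and about 10% dropout. Evaluable per arm: 30 × 0.9 = 27. Noncentral t with 52 df and noncentrality 0.59 × √(27/2) gives 80.8%. The figure reproduces and is not in dispute.

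**2. Inputs the documents do not give.** There is no inability rate, ORS SD or correlation between visits. All of the following are assumptions: SD of change 0.75 for EDSS, 0.25 for log T25FW and 0.16 for log 9HPT; correlation 0.3 between components and 0.4 to 0.8 between visits; active arm 0.45 SD better at Week 52, building linearly; SD of log baseline T25FW 0.45. Scored with the SAP 4.3.1 thresholds, this gives a true Week 52 difference of about 0.83 ORS points and an SD of about 1.40, so ES is about 0.59.

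**3. Inability.** It is applied to the Week 52 T25FW with one threshold for both arms, either on the change in walk time or on the absolute walk time, set to give a chosen placebo rate. Truth scores an unable walk as -1. The MMRM is represented by regressing Week 52 ORS on arm, earlier ORS and baseline values in subjects with ORS observed, then averaging over each arm. There were 200,000 subjects per arm.

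| Unable, placebo (active) | Share of true effect lost, MMRM | ORS points | Share lost, MI |
|---|---|---|---|
| 5% (2-3%) | 0.9-4.7% | 0.01-0.04 | 0.5-2.4% |
| 10% (4-7%) | 1.4-8.7% | 0.01-0.07 | 0.7-4.8% |
| 15% (7-11%) | 1.9-12.7% | 0.02-0.11 | 1.1-7.5% |

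A repeat run gave 4.8%, 8.9% and 12.9% for the worst case (change threshold, visit correlation 0.4).

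**4. Direction.** With no drug effect the bias was essentially zero. With a harmful drug (active 0.45 SD worse, 10% placebo inability, change threshold, visit correlation 0.4) a true difference of -0.83 was estimated as -0.72. The pull is toward zero in both directions.

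**5. Power.** Blanking removes low scores, so the SD shrinks as well. ES after blanking = 0.59 × (1 - loss) × 1.40 / new SD, with n held at 27. In the worst case:
- 5%: 0.59 × 0.952 × 1.40/1.37 = 0.574, power 79%
- 10%: 0.59 × 0.911 × 1.40/1.33 = 0.566, power 78%
- 15%: 0.59 × 0.871 × 1.40/1.30 = 0.553, power 77%

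At visit correlation 0.8, ES does not fall and no power is lost.

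**6. A second model.** Here inability can arise on the walk or either peg test and then persists. With about 7% unable on placebo and 2% on active, the difference was 0.83 with blanking against 0.91 with every measured score kept. ES moved only from 0.61 to 0.60.

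**7. How many subjects.** At 5%, 27 × 0.05 = 1.35 placebo subjects are expected, and the chance of none is 0.95^27 = 0.25.

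**The case against.** The strongest reply is that SAP 4.3.1 says what happens when a component is missing, not that an attempted but uncompleted test counts as missing. Protocol Appendix D places the activity details in the Operations Manual, and SAP 11.1 refers to a statistical programming plan. Either may already score such a test, and then the point falls. This stands, and it is why the point is conditional.

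A reader might infer that same-day EDSS worsening vanishes from the report. It does not. SAP 9.6 plots each component's category as observed, and SAP 9.4.2 analyses progression by component. What is missing is an ORS analysis that reflects it without assuming MAR.

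A reader might also infer that power falls in line with the ORS points lost. That holds the SD fixed, while blanking reduces it, so the fall is much smaller.

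Finally, Protocol Appendix E reports that all subjects had completed 52 weeks by January 2021 and that a planned efficacy analysis had found no benefit. Changing the primary scoring afterwards would be post hoc. That is right, and it limits what the fix can be.

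**Conclusion.** The gap is real but minor. If no other document scores an undoable test, the plan discards worsening because of the outcome itself, and neither specified ORS analysis relaxes MAR.

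Where inability follows function, a real benefit is understated; a real harm is also understated, which favours the drug. With no effect there is essentially no bias. A reader might infer that the rule manufactures a benefit, or that it explains the reported lack of efficacy. The documents support neither: the pull is toward zero, and it is small on every set of assumptions tried.

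The sizes above rest wholly on assumed SDs, correlations and inability rates, and on one inability threshold for both arms. They would not carry over if inability arose in one arm for reasons unrelated to function. At low inability rates the effect may be negligible.

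**What to change.** In SAP 4.3.1, cite the existing rule if the Operations Manual or statistical programming plan has one. Otherwise score a T25FW or 9HPT not completed because of MS-related physical inability as -1 for that component, and set the ORS to missing only when a component is missing for another reason.

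If test-level reasons were not collected (SAP 8.5 shows reasons for visits only), or if treatment codes are already open, leave the primary analysis as specified. Run this scoring as a labelled sensitivity analysis of the Week 52 ORS beside the MMRM and the MI. Classify the reasons without knowledge of treatment, and call the analysis post hoc if it follows unblinding.

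Cost: SAP wording, a review of reasons for missing tests that needs some judgement, and one extra analysis. No new subjects or assessments.

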4.3.4 Safety Endpoints

Safety variables include adverse events (AEs), serious adverse events (SAEs), adverse events of special interest (AESI), vital sign measurements (including pre- and post-infusion blood pressure), MS relapses, electrocardiogram (ECG) variables, Columbia-Suicide Severity Rating Scale (C-SSRS) assessments, and clinical laboratory testing (hematology, chemistry, and urinalysis) as measures of safety and tolerability for the entire study duration.

4.4 Sample Size Justification

Approximately 90 subjects will be equally randomized 1:1:1 to each treatment group (approximately 30 subjects in each treatment, with at least 20 PPMS subjects and approximately 10 nrSPMS subjects). There is limited prior data to estimate the magnitude of effect and variance. This sample size will have approximately 80% power to detect an effect size (ES) of 0.59 with significance level of 0.1 and overall dropout rate of approximately 10%, using a 1-sided t-test.

